10.5 Visit 2: Baseline assessment and randomisation

- Complete eligibility assessment.
- Answer any questions about trial.
- Review concomitant medication and record compression system in use.
- Carry out assessments of health-related quality of life (RAND 36, EQ5D, and CXVUQ).
- Measure ulcer size and obtain history of duration from participant
- Randomise participant.
- Give participant allocated trial treatment.

10.6 Visit 3: 24 weeks after randomisation

- Determine if reference ulcer healed
- Obtain date healed from clinical record if healed
- Review concomitant medication and record compression system in use.
- Obtain remaining trial medication and count capsules.
- Carry out assessments of health-related quality of life (RAND 36, EQ5D, and CXVUQ).
- Assess blinding.
- Complete an "End of Trial Participant" survey to give feed-back on their trial experience.

11. Statistical Considerations

11.1 Sample Size

We estimate that 354 participants will be required. A sample size of 318 would be sufficient to show a **four week** difference in time-to-healing at 90% power with an alpha of 0.05, assuming the median time-to-healing in the control group over a six month follow up is 92 days (the median time to healing suggested by a previous bandaging trial for VLU patients over 24 weeks).⁶⁰ These data equate to a hazard ratio for VLU healing of 1.45, which is smaller than that suggested by our re-analysis of data from a cohort in a previous VLU trial (hazard ratio for VLU healing 1.77 for 150 mg dose). A four week difference was the minimal important difference that would most frequently

persuade people to use aspirin in a small commissioned survey of older people in Auckland, was the time interval used in a Canadian venous ulcer trial (<http://clinicaltrials.gov/ct2/show/study/NCT00202267>) and is lower than clinically significant differences used to calculate the sample sizes in two large venous ulcer trials conducted in the United Kingdom (the VenUS II and III trials^{61,62}). Although both the HALT trial and the PREPARE Pilot achieved very high follow up rates (99% and 100%),^{8,34} we have allowed for 10% loss to follow up, and thus a sample of 354 (177 in each group) will be required. Even if recruitment were lower than anticipated, using the same assumptions as above, a sample of 238 inflated to 264 (132 in each group) to allow for 10% loss to follow up would be sufficient to show a four week difference in time to healing with 80% power with an alpha of 0.05.

We assume that 70% of patients presenting with leg ulcers to the trial centres will have VLU. This assumption is supported in the literature^{5,6} and in an audit of patients presenting to the Nurse Maude Association in Christchurch in 2010 (pers. comm., [name], see below).

- In Auckland DHB, the most recent data (2011) shows the service received 309 referrals from multiple sources (mainly general practitioner and internal sources). Extrapolating this data to the 18 month recruitment period, Auckland DHB would receive 463 new assessment requests of which 324 new patients would have VLU, assuming 70% of these referrals had venous ulceration.
- In Christchurch, reorganisation of services since the Earthquake has increased the number of people with wounds now seen at Nurse Maude. Between November 2012 and October 2013, 999 new patients were seen and analysis suggested 499 had VLU (pers. comm, [name], November 2013). This is a substantial increase over 2010 when Nurse Maude undertook 426 new assessments on patients with leg ulcers and 297 patients (69.7%) were assessed as having VLU (pers. comm., [name], Nurse Practitioner). Rather than use the more recent data, we have used the 2010 data to ensure recruitment is justified even with conservative estimates. Extrapolating the 2010 data to the 18 month recruitment period, Nurse Maude would receive 639 new assessment requests of which 447 new patients would have VLU, assuming 70% of new assessments had venous ulceration. If the 2012-13 data is correct, ~750 patients would have VLU.
- In Counties Manukau DHB, the district nursing service undertook 212 new Doppler ultrasound assessments on patients with leg ulcers in 2010 (pers. comm., [name], Nurse Specialist). No data is available on how many patients were assessed as having VLU, or how many patients received compression therapy. Extrapolating the data on assessments to the 18 month recruitment period, Counties Manukau DHB would receive 318 new assessment requests, of which 222 new patients would have VLU assuming 70% of new assessments had venous ulceration.
- In Southern DHB (Dunedin), the leg ulcer clinic treats about 120 patients per year with compression (pers. comm., [name], Nurse Specialist, Oct 2013). Extrapolating the data on compression to the 18 month recruitment period, Southern DHB would have 180 patients with VLU.
- In Waikato DHB, the district nursing services put an average of 14 new patients per month into compression for VLU (pers. comm., [name], Nurse Practitioner, Oct 2013). Extrapolating the data on compression to the 18 month recruitment period, Waikato DHB would have 252 new patients with VLU.

Based on these data around **1425** new patients with VLU are likely to present to the above services during the 18 month recruitment period. Data from the HALT trial and the recent audit at Christchurch support the assumption that 30% will be using aspirin and an additional 10% will be using other anticoagulant medications, making these patients ineligible. Assuming therefore that around 40% of patients will be ineligible on these bases, a pool of **855** new patients with VLU would be eligible to take part in the proposed trial. The recruitment pool will be greater when prevalent cases at the start of the trial are considered for inclusion. We are confident that high participation rates are readily achievable, based on our past experience showing VLU patients are highly motivated to participate in research in New Zealand. The recruitment rate in the HALT trial was 93%, in the Auckland Leg Ulcer Study 68%, and in the PREPARE pilot 100% of those registered.

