- Confirmation with participant's general practitioner that the participant can take low dose aspirin or placebo.

Potentially eligible participants will be *excluded* if they meet any of the criteria below:

- Pregnant or breast-feeding women
- History of myocardial infarction, stroke, transient ischaemic attack, angina or significant peripheral arterial disease
- History of adverse effects related to aspirin use

- Currently using aspirin, or other anti-platelet or anticoagulant therapy
- Participant has any other existing condition or treatment that is a contraindication to use of aspirin or to participation in the trial
- Participant has any other existing condition where treatment with aspirin is indicated.

Test Product:

- Aspirin 150 mg daily + compression bandaging

Reference Therapy:

- Placebo daily + compression bandaging

Primary Outcome:

Time to complete healing over 24 weeks. Complete healing is defined as full epithelialisation of the ulcer with no scab.

Secondary outcomes:

- Proportion with healed reference VLU at 24 weeks
- Change in estimated reference ulcer area from baseline to 24 weeks
- Adherence with aspirin
- Change in health-related quality of life from baseline to 24 weeks
- Adverse events
- Efficacy of blinding.

Sample size: A sample size of 354 (177 in each group) will be sufficient to show a **four week** difference in time-to-healing at 90% power with an alpha of 0.05, assuming the median time-to-healing in the control group over a six month follow up is 92 days and allowing for 10% loss to follow up.

Statistical analysis: All analyses will use intention-to-treat in accord with a Statistical Analysis Plan developed *a priori*. Time-to-event data will be analysed using Kaplan Meier plots, log rank test and Cox regression. Simple incidence rates, relative risks and 95% CIs will be obtained for all binary variables in the first instance, with multiple logistic regression analysis if necessary to adjust for imbalance. Continuous outcomes will be analysed using multiple linear regression and adjusted for baseline value and other covariates if needed. A *kappa* will be calculated for the evaluation of the efficacy of blinding.

2. Background

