6.1 Recruitment source & process

Patients with venous leg ulcers who present for treatment to or already receiving treatment from the community-based district nursing services at trial centres previously involved in the National Institute of Health Innovation's (NIHI) leg ulcer trials will be recruited. These centres are based within Auckland, Counties Manukau, Waikato, and Southern District Health Boards, and Nurse Maude community nursing services in Christchurch. The same model of recruitment is used as was successfully employed in previous venous leg ulcer trials in New Zealand (figure 4). A 0.5 FTE Research Nurse will be seconded to the trial from each trial centre (employing authority will be reimbursed).

The District Nurse will identify potential participants, obtain verbal consent from them to be contacted by the Research Nurse if the patient is interested in the trial and notify the research nurse at each trial centre. The Research Nurse will screen the patients for eligibility. Eligible patients will be consented, assessed, and randomised by the Research Nurse at a location convenient to the patient. The location may be a clinic, the patient's home or workplace. Once randomised, the participant will receive the allocated treatment from the Research Nurse, who will also conduct the endpoint visits at 24 weeks after randomisation, again at a location convenient to the participant. In between Research Nurse visits the participants will continue to receive normal care by the District Nurses.

[figure not shown]

Figure 3: Flow chart of proposed study.

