9.1 Primary outcome measure

Time to complete healing (defined as intact skin without a scab) is recommended as an outcome to be included in research by the Cochrane Collaboration Wound Review Group and a 24 week follow up period is considered a minimum. Time to event data will be obtained from clinical records. District nurses visit patients on a weekly basis as part of normal care and record healing (average number of district nurse visits was 1.1 per week in the HALT trial). At 24 weeks, the Research Nurse will determine if the reference ulcer is healed. If the reference ulcer is healed, the research nurses will access clinical records to determine the date of healing was first reported during the 24-week period. If the reference ulcer is unhealed, the Research Nurse will determine from the clinical record whether the reference ulcer had healed at any time prior to 24 weeks. If there is no mention of healing then the ulcer will be assumed to have been unhealed during the 24 weeks. If the reference ulcer is recorded as healed during that time, the unhealed ulcer will be assumed to be a recurrent ulcer and the date healing is first recorded will be assumed to be the healing date.

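### With follow-up fixed at 24 weeks, 354 and 264 randomised give about 81–83% and 69–72% power after 10% loss, not the stated 90% and 80%

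*Protocol*

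**What the plan says.** Section 11.1 takes a control median time to healing of 92 days, a four-week difference and an alpha of 0.05. From these it derives 318 participants for 90% power and adds an allowance for loss: "we have allowed for 10% loss to follow up, and thus a sample of 354 (177 in each group) will be required". The synopsis repeats the claim: "A sample size of 354 (177 in each group) will be sufficient to show a" four-week difference at 90% power. On the effect size, section 11.1 says "These data equate to a hazard ratio for VLU healing of 1.45". If recruitment falls short, "a sample of 238 inflated to 264 (132 in each group) to allow for 10% loss to follow up would be sufficient" for the same difference at 80% power. No formula, event probability or expected number of healings is given.

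Follow-up is the same fixed length for everyone. The primary outcome is "Time to complete healing over 24 weeks". Section 6.1 gives the research nurse the final assessment, "who will also conduct the endpoint visits at 24 weeks after randomisation". Section 9.1 closes the observation window at that point: "If there is no mention of healing then the ulcer will be assumed to have been unhealed during the 24 weeks". Section 11.2.4 says that, in the main analyses, anyone lost to follow-up is taken to be unhealed.

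**The concern.** The power of a log-rank or Cox analysis depends on the number of healing events, not on the number of participants. A sample size for 24-week follow-up must therefore be larger than the required event count, because some ulcers will still be open at week 24. The stated 318 and 238 are almost exactly the required event counts, so nothing appears to have been added for ulcers that stay open.

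The loss allowance has a separate problem. Dividing by 0.9 treats lost participants as removed, whereas section 11.2.4 keeps them in the analysis as non-healers, which dilutes the effect.

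What is at stake is the chance of missing a difference the protocol itself calls minimally important. A null result would be read as stronger evidence against a four-week benefit than the design supports. The fallback sentence could also be used to justify closing recruitment at 264.

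**Working it through.** **Inputs.** From section 11.1: control median 92 days; four-week difference, so an aspirin median of 92 − 28 = 64 days; hazard ratio (HR) 1.45; alpha 0.05; equal allocation; 10% loss. Follow-up is 24 weeks = 168 days (synopsis, sections 6.1 and 9.1).

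Two assumptions are mine:
- Healing times are exponential. This is the simplest basis for turning two medians into one hazard ratio.
- The test is two-sided. The protocol does not say, but 318/238 = 1.336 matches the two-sided ratio for 90% against 80% power (1.339) and not the one-sided ratio (1.385).

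The ratio of medians is 92/64 = 1.4375, slightly below the stated 1.45. Ranges below run from HR 1.4375 to HR 1.45.

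**Step 1: reproduce the stated figures.** Schoenfeld's required events for 1:1 allocation are 4(z₀.₉₇₅ + z_power)² / (ln HR)².

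| HR | Events for 90% | Events for 80% |
|---|---|---|
| 1.4375 | 319.1 | 238.4 |
| 1.45 | 304.4 | 227.4 |

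The first row is the protocol's 318 and 238 to within rounding. Then 318/0.9 = 353.3 and 238/0.9 = 264.4, so the inflation to 354 and 264 is arithmetically sound.

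A second route also lands there. Take HR 1.45, uniform entry over 18 months (section 11.1 speaks of patients presenting "during the 18 month recruitment period") and a further six months to a common end date. The mean event probability is then 0.959, giving 304.4/0.959 ≈ 318 and 227.4/0.959 ≈ 237. Which route was used is not known, and neither matches fixed 24-week follow-up.

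The event probability that 318 needs for 90% power is 304.4/318 = 0.957 at HR 1.45 and 319.1/318 ≈ 1.00 at HR 1.4375. For 238 and 80% it is 0.955 and 1.00.

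**Step 2: healing expected by day 168.**
- Control: 1 − 0.5^(168/92) = 71.8%.
- Aspirin: 1 − 0.5^(168/64) = 83.8%.
- Mean: 77.8% (77.9% at HR 1.45).

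Section 15 of the protocol is less optimistic: it suggests aspirin could bring healing to 75% at 24 weeks.

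**Step 3: power.** Power = Φ(½·√events·ln HR − 1.96). For 318 evaluable at HR 1.4375, events = 318 × 0.778 = 247.4, and Φ(½ × 15.73 × 0.3629 − 1.96) = Φ(0.894) = 81.4%.

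| Analysed | Expected events | Power, HR 1.4375 | Power, HR 1.45 | Stated |
|---|---|---|---|---|
| 318 (354 less 10%) | 247–248 | 81.4% | 83.3% | 90% |
| 354, no loss | 275–276 | 85.3% | 87.0% | – |
| 238 (264 less 10%) | 185 | 69.5% | 71.6% | 80% |
| 264, no loss | 205–206 | 73.9% | 75.9% | – |

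Reading six months as 182 days gives 83–84% for 318 and 71–73% for 238.

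**Step 4: the rule in section 11.2.4.** Simulated log-rank tests (10,000 replicates per case):

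| Handling of the lost | 354 randomised | 264 randomised |
|---|---|---|
| 10% lost, all counted unhealed to day 168 | 70.1–72.6% | 56.9–60.2% |
| 10% lost, unhealed only from the time of loss | 81.7–82.9% | 69.4–72.1% |
| 1% lost, all counted unhealed to day 168 | 83.4–85.5% | 71.7–74.7% |

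**Step 5: detectable difference.** For 90% power under 24-week follow-up, the difference must be 31 days (HR 1.51) with 318 evaluable, or 30 days (HR 1.48) with 354 and no loss.

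**The case against.** **The literal reading of section 11.2.4 is a worst case.** It needs the full 10% loss and discards healings already in the clinical record. Section 9.1 takes healing dates from those records, so a healing documented before loss would normally be kept. Power is then about the same as with the lost removed. Section 11.1 also cites 99% and 100% follow-up in earlier trials. This stands: 70–73% and 57–60% are the low end, and the wording of section 11.2.4 does not settle which reading applies. The main shortfall does not depend on it, since it remains with no loss at all.

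**The exponential shape is assumed.** With medians held at 92 and 64 days, a Weibull shape of 1.2 gives 94% for 318 and 86% for 238, while a shape of 0.8 gives about 60% and 48%. The result is therefore sensitive to shape if only the four-week difference is fixed. But a shape of 1.2 implies an HR of 1.4375^1.2 ≈ 1.55, which contradicts the protocol's 1.45. With HR held at 1.45, shapes from 0.8 to 1.2 give 81–85% and 69–74%, so the shortfall remains.

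**Alpha might be one-sided.** At HR 1.45 with 24-week censoring, a one-sided test gives 90% for 318 and 81% for 238. The ratio of the two stated sizes argues against that reading, as do the planned 95% confidence intervals, but the protocol should say which applies.

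**The practical loss is modest.** With 10% removed, 354 still exceeds 80% power, and at the HR of 1.77 from the earlier cohort even 238 evaluable would give over 97%. That is true, but it does not make the stated 90% and 80% correct for the difference the protocol chose.

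**Conclusion.** The concern holds. The stated 318 and 238 give the claimed power only if nearly every evaluable participant heals under observation; the protocol's own medians and 24-week window imply about 78%. At the planned difference the risk of a false negative is:

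| Randomised | Stated | No loss | 10% lost, removed | 10% lost, all counted unhealed |
|---|---|---|---|---|
| 354 | 10% | 13–15% | 17–19% | 27–30% |
| 264 | 20% | 24–26% | 28–31% | 40–43% |

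This rests on exponential healing, a two-sided 5% test and an HR between 1.4375 and 1.45. The last column also depends on reading section 11.2.4 literally. The gap between 1.44 and 1.45 is minor.

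**What to change.** In section 11.1 and the synopsis:
- State the formula, the sidedness of alpha, the hazard ratio used, the assumed healing-time distribution, the observation time per participant, the event probability and the expected number of healings.
- Restate the power of 354 and 264 for 24-week follow-up, once with losses removed (about 81–83% and 69–72%) and once under section 11.2.4. For the latter, say whether healing recorded before loss counts: about 82–83% and 69–72% if it does, about 70–73% and 57–60% if it does not.
- Withdraw the statement that 264 is sufficient for 80% power.
- Reconcile the HR of 1.45 with 92/64 = 1.44.

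The cost is wording, and a less favourable power statement. Correcting the text needs no additional participants, visits or data.

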11.2 Statistical Analysis

All statistical analyses will be performed using SAS version 9.3 (SAS Institute Inc. Cary NC) Data analyses will be specified *a priori* in a statistical analysis plan (SAP) prepared by the trial statistician (and agreed upon by all members of the Steering Committee). The SAP will be available as a public domain document. Data from the Case Record Forms (CRFs) will be entered into password secured Oracle databases hosted by NIHI via the web by the Research Nurse. The data will be extracted into SAS for analysis on the trial's completion. No interim analyses are planned.

11.2.1 Baseline Characteristics

Data on demographic characteristics (sex, age, self-reported ethnicity), history of ulceration, ulcer size, clinical history, current treatments (including compression system) and health-related quality of life will be collected. Since any differences between randomised groups at baseline could only have occurred by chance, no formal significance testing will be conducted.

11.2.2 Treatment effect

All data analyses will be carried out on an intention-to-treat basis⁶³. Time-to-event data will be analysed using Kaplan Meier plots and log rank test, and Cox regression will be used to take into account known covariates and the varying times since randomisation. The assumption of proportionality will be checked using standard graphical techniques. Simple incidence rates, relative risks, absolute risks and numbers needed to treat, and 95% CIs will be obtained for all binary outcomes in the first instance, with subsequent multiple logistic regression analysis conducted if necessary to adjust for imbalance in covariates. Continuous outcomes will be analysed using multiple linear regression and adjusted for baseline value and other covariates if needed. Adverse events will be analysed using incidence rate ratios. A *kappa* will be calculated for the evaluation of the efficacy of blinding. Should aspirin prove effective in the primary analysis, heterogeneity of effects on time to healing will be analysed using subgroups specified *a priori* in the Statistical Analysis Plan.

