2.8 Rationale for a clinical trial

The ageing population and substantial anticipated increase in people with VLU (especially in the very old), the need for cheap, accessible adjuvant treatments, the role of platelets in the pathophysiology of VLU and the encouraging evidence for aspirin all point to the need for a definitive randomised controlled trial of low dose aspirin as an adjuvant treatment for VLU using a trial population that is as open as clinically possible and thus similar to that encountered every day in clinical practice.

[figure not shown]
3. Objectives

The main aim of this trial is to evaluate the effectiveness of low dose aspirin compared to placebo when used in addition to compression therapy for VLU time-to-healing over 24 weeks follow up. Other aims include estimating the effect of aspirin on proportion of patients healed, adverse events, adherence and health-related quality of life (HRQoL).

4. Trial Design

A prospective community-based, double-blind, placebo-controlled, randomised trial with participants receiving either 150 mg aspirin daily for up to 24 weeks or matching placebo. Block randomisation will be used, stratified by trial centre and prognostic index (ulcer size and duration) to ensure a balance of participants within trial centres and for participants likely to be slow healers. Participants in both arms will also receive compression therapy (with system of choice guided by patient and/or clinical preference) as delivered through district nursing services at the trial centres. The district nurse will identify potential participants, obtain verbal consent from them to be contacted by the research nurse if the patient is interested in the trial and notify the research nurse at each trial centre.

5. Trial Plan Schematic

6. Recruitment

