6.3 Eligibility criteria

Patients with leg ulcers will be eligible for *inclusion* if they meet the following criteria:

- Aged 18 years or older
- Determined to have a venous leg ulcer (clinical indications of venous ulceration, ABI \geq 0.8, and other causative aetiologies ruled out)
- Able to tolerate compression therapy
- Able to provide written informed consent
- Confirmation with participant's general practitioner that the participant can take low dose aspirin or placebo.

Potentially eligible participants will be *excluded* if they meet any of the criteria below:

- Pregnant or breast-feeding women
- History of myocardial infarction, stroke, transient ischaemic attack, angina or significant peripheral arterial disease
- History of adverse effects related to aspirin use
- Currently using aspirin, or other anti-platelet or anticoagulant therapy
- Participant has any other existing condition or treatment that is a contraindication to use of aspirin or to participation in the trial
- Participant has any other existing condition where treatment with aspirin is indicated.

7. Randomisation and allocation concealment

On registration (week -1) participants will be assigned a unique sequential registration number using numbers generated by the NIHI data management. When a registration number has been allocated, the participant's initials and date of birth and the date of registration must be recorded. This registration number will be used to identify the participant throughout all periods of the trial. Once a registration number has been assigned, it may not be used again.

Immediately after baseline data have been recorded, consented patients who fulfil entry criteria will be randomised by computer to one of the two trial groups using stratified blocked randomisation with varying block sizes of 2 and 4. The randomisation sequence will be prepared by the trial statistician and loaded into a secure database. Randomisation will be stratified by trial centre and prognostic index (based on ulcer and duration) which will isolate any centre effect in clinical management and ensure a balance on key prognostic variables known to influence healing at 24 weeks. Each treatment pack is uniquely numbered and is allocated using the randomisation sequence. The Research Nurse accesses the randomisation web-page, completes data entry, and generates the allocation using a computerised tablet. The allocated treatment is then given to the participant by the Research Nurse.

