10.1 Baseline assessments

Screening information will be obtained from a telephone contact with the patient at week -1. Eligible patients will be visited at Week -1 and, once consented, the following baseline data will be collected immediately prior to randomisation:

- Demography: age, sex, self-reported ethnicity.
- Ulcer area and duration: Reference VLU area (area > 5 cm²) and duration (duration for > six months) provide data for a prognostic index for VLU healing with 24 weeks of compression.⁵⁸ The index assigns scores of 0, 1 or 2 based on absence of both factors, presence of one factor, or presence of both factors. Sophisticated tools for measuring ulcer area are either too expensive (e.g. SilhouetteTM) or no longer supported by the manufacturer in New Zealand (e.g. VisitrakTM). A simpler method of estimation using the formula for area of an ellipse has been shown to be highly correlated with ulcer area, both in the literature ($r = 0.951$)⁵⁰ and internal data from one of our previous trials ($r = 0.92$).⁸ Ulcer duration will be obtained from patient recall. Where more than one VLU is present, the largest ulcer will be the reference ulcer.
- ABI: An ABI < 0.8 indicates that there is a high probability that some arterial insufficiency is present (positive predictive value = 95% in a general practice population).⁵⁹ Use of compression therapy where significant arterial disease is present can result in severe ischaemia in the leg,

with risk of necrosis. Consequently ABIs are routinely obtained for all patients with incident ulcers under the care of each of the trial centres taking part in the proposed trial, to confirm suitability for compression therapy. An ABI will be obtained from the clinical records for each participant. Where a potential participant already in treatment has an ABI obtained more than three months prior to the eligibility screen, a new ABI will be obtained prior to inclusion to ensure no development or progression of arterial disease.

- Clinical history and concomitant medications.
- Compression system: Details of the patient’s current treatment regime will be recorded.
- Health-related quality of life (HRQoL) instruments: The RAND 36-item Health Survey⁵¹, EQ5D,⁵⁴ and the Charing Cross Venous Ulcer Questionnaire (CXVUQ)⁵² will be administered.

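### The log-rank test named for time to healing has no strata, although randomisation is stratified by centre and a prognostic index; stratifying it would protect power at almost no cost

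*Protocol*

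**What the plan says.** The primary outcome is "Time to complete healing over 24 weeks". The statistical paragraph of the synopsis reads "Time-to-event data will be analysed using Kaplan Meier plots, log rank test and Cox regression". Section 11.2.2 plans "Kaplan Meier plots and log rank test, and Cox regression will be used to take into account known covariates". The log-rank test has no strata in either place, and the Cox covariates are not listed.

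The protocol treats the randomisation factors as important for healing:
- Section 7 stratifies by centre and prognostic index to "isolate any centre effect in clinical management and ensure a balance on key prognostic variables known to influence healing at 24 weeks".
- Section 4 gives the aim as to "ensure a balance of participants within trial centres and for participants likely to be slow healers".
- Section 10.1 explains that ulcer area and duration "provide data for a prognostic index for VLU healing with 24 weeks of compression". The score is 0, 1 or 2 according to how many of two factors are present: area above 5 cm² and duration above six months.

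Section 11.2.2 closes with "Should aspirin prove effective in the primary analysis, heterogeneity of effects on time to healing will be analysed using subgroups", without saying which analysis is the primary one. Section 11.2 refers analysis detail to a statistical analysis plan, which is not at hand.

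**The concern.** Stratified randomisation balances the arms on the index. A log-rank test that ignores the index then gives away power in two ways:
- Its variance allows for chance imbalance between the arms that the design has largely removed, so the test is conservative.
- Pooling patients who heal at different speeds dilutes the treatment contrast. Fast healers leave the risk set sooner on the better treatment, so the pooled hazard ratio drifts towards 1 even when the ratio within each score is constant.

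Both effects grow with the prognostic strength of the index. What is at stake is power for the single primary outcome, not validity.

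**Working it through.** **The protocol's own figure.** Schoenfeld events for HR 1.45, 90% power and two-sided 0.05: 4 × (1.960 + 1.282)² / (ln 1.45)² = 304.4. The stated 318 follows if 18 months of accrual plus 6 months of further follow-up are assumed: mean healing probability 0.9586, 304.4 / 0.9586 = 317.6. Then 318 / 0.9 = 353.3, so 354.

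With each patient followed for 168 days, healing probabilities are 1 − 2^(−168/92) = 0.718 on control and 1 − 2^(−1.45 × 168/92) = 0.840 on aspirin. That gives about 318 × 0.779 = 248 events and power of about 83%. The shortfall from 90% is a separate matter. Only the gaps between tests matter here.

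**Inputs from the protocol.** 318 evaluable patients, HR 1.45 (taken as the ratio within strata), control median 92 days, censoring at day 168, blocks of 2 and 4, 5 centres × 3 scores = 15 cells.

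**Inputs assumed.** Shares of scores 0/1/2; a multiplier r on the healing hazard per index point; five equal centres with log-hazard SD 0.2; exponential healing within strata. The baseline rate is solved so that the control mixture has median 92 days.

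**Tests.** In each stratum s, U_s = Σ(observed − expected healings on aspirin), with hypergeometric variance V_s. The stratified test compares (ΣU_s)² / ΣV_s with 3.841. The unstratified test treats all patients as one stratum.

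**Power (%), 5000 simulated trials per scenario, Monte Carlo SE at most 0.7.**

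| Shares 0/1/2 | r | No strata | Index strata | Index × centre | Gain, index | Gain, both |
|---|---|---|---|---|---|---|
| 40/40/20 | 1 | 83.0 | 82.8 | 82.1 | −0.2 | −0.9 |
| 40/40/20 | 0.7 | 78.2 | 80.4 | 80.0 | 2.2 | 1.8 |
| 40/40/20 | 0.5 | 72.0 | 81.2 | 80.4 | 9.2 | 8.4 |
| 33/33/33 | 1 | 82.5 | 82.0 | 82.0 | −0.5 | −0.5 |
| 33/33/33 | 0.7 | 78.2 | 81.0 | 79.9 | 2.8 | 1.7 |
| 33/33/33 | 0.5 | 67.9 | 79.3 | 78.2 | 11.4 | 10.3 |
| 55/35/10 | 1 | 82.1 | 81.7 | 81.2 | −0.4 | −0.9 |
| 55/35/10 | 0.7 | 79.9 | 81.9 | 81.1 | 2.0 | 1.2 |
| 55/35/10 | 0.5 | 74.7 | 81.5 | 81.1 | 6.8 | 6.4 |

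To judge the multipliers: at shares 40/40/20, control healing by 24 weeks for scores 0/1/2 would be 81/69/56% at r = 0.7 and 88/65/41% at r = 0.5.

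**Type I error.** Unstratified: 4.5–4.9% (r = 1), 4.2–4.7% (0.7), 3.2–4.0% (0.5). Index-stratified: 4.4–5.4% throughout.

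**Second simulation** (shares 45/35/20, 4000 trials, strata of index × centre). Power without and with strata was 83.5 v 81.5% with no strata effects, 77.6 v 80.8% at r = 0.6 and 62.7 v 78.3% at r = 0.4. Type I error was 5.5 v 5.5%, 4.0 v 5.0% and 2.7 v 5.7% (SE about 0.3–0.4).

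**Third simulation** (shares 40/40/20, index strata). Power was 82.0 v 81.6% (r = 1), 77.5 v 79.2% (0.7) and 70.8 v 79.5% (0.5). Direction and size agree across all three.

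**The case against.** The strongest reply is that this is detail for the statistical analysis plan. The protocol never says the log-rank test is to be unstratified; it names the test and leaves its form open. Strata, Cox terms and the choice of deciding test are ordinary content of that plan, to which Section 11.2 defers. This stands in part: the missing covariate list and the unnamed deciding test are not faults of the protocol. What remains is that the test is named twice without the strata that Section 7 has already fixed, so adding them is a plain improvement.

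A reader might infer that no planned analysis uses the randomisation factors. The document does not support that. The Cox model is there to account for known covariates, and Section 7 describes the index variables as known to influence healing. Section 2.5 also reports an earlier aspirin hazard ratio adjusted for ulcer size and duration, the two components of the index.

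A reader might also infer that naming two methods, or ignoring the strata, seriously inflates false positives. Ignoring the strata makes the test conservative. Even if whichever of the unstratified log-rank and an index-adjusted Cox model came out significant were taken, the simulated type I error is only 5.3–6.0%.

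Finally, the loss of power depends wholly on assumed index strength and shares. That is correct, and the range must be read that way.

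**Conclusion.** The point holds as an inexpensive improvement that should be made, with medium confidence. If the log-rank test is run as named, it is conservative and less powerful than a stratified test whenever the index is prognostic, as the protocol says it is.

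Against index strata the loss is nil at r = 1, about 2–3 points at r = 0.7 and about 7–11 points at r = 0.5. Against strata for both factors it is 1.2–1.8 points at 0.7 and 6.4–10.3 at 0.5. These figures assume a constant hazard ratio of 1.45 within strata, exponential healing, and the shares and centre effects listed above. The upper end should not be read as this trial's expected loss, because the protocol gives nothing from which to choose r.

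**What to change.** In the synopsis and Section 11.2.2, replace the bare log-rank test with: *log-rank test stratified by the randomisation factors (prognostic index and trial centre)*. Take the hazard ratio from a Cox model with treatment as the covariate, stratified by the same factors. Apart from the handling of ties, its score test is the stratified log-rank test, so test and estimate match. Keep the unstratified log-rank test as supportive. As a minor clarification, let the primary analysis mentioned in the last sentence of Section 11.2.2 refer to this one.

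The change is wording only, since both factors are recorded at randomisation. With 15 cells, 318 patients average 318 / 15 = 21 per cell, so sparse cells cost little. If the factors turn out not to be prognostic, the cost is about 0–2 points of power: 0.5–0.9 in the first simulation and 2.0 in the second.
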